1 SYNOPSIS

Name of Sponsor/Company: Acer Therapeutics Inc.
Name of Investigational Product: ACER-801
Name of Active Ingredient: Osanetant
Title of Study: A Phase 2a Randomized, Double-Blind, Placebo-Controlled, Dose-Ranging Study to Evaluate the Efficacy, Safety, and Pharmacokinetics of ACER-801 for Treatment of Moderate to Severe Vasomotor Symptoms (VMS) Associated with Menopause
Principal Investigator: [name]
Investigational Site: Spaulding Clinical Research, LLC
Phase of Development: Phase 2a
Study Objectives: Primary Objective: The primary objectives are to: 
• Evaluate the pharmacokinetic (PK) profile of ACER-801 and its metabolite at different doses• Evaluate the safety profile of ACER-801 at different doses Secondary Objectives: The secondary objectives are to: 
• Evaluate the effect of ACER-801 at different doses on the frequency of vasomotor symptoms associated with menopause compared to placebo• Evaluate the effect of ACER-801 at different doses on the severity of vasomotor symptoms associated with menopause compared to placebo• Evaluate the effect of ACER-801 at different doses on the hot flash severity score compared to placebo Exploratory Objectives: The exploratory objectives of this study are to evaluate: 
• The effect of ACER-801 at different doses on change in hormones compared to placebo including:
• luteinizing hormone (LH)• follicle stimulating hormone (FSH)• estradiol• testosterone• sex hormone binding globulin (SHBG)• adrenocorticotropic hormone (ACTH)• cortisol• thyroid-stimulating hormone (TSH)• triiodothyronine (T3) (Total and Free)• thyroxine (T4) (Total and Free)• Changes in the number of night-time awakenings (NTA)• Changes in blood bone density marker concentration• Changes in blood markers associated with stress• Changes in electrocardiogram (ECG) variables (heart rate, RR, PR, QRS, QT, QTcF, and QTcB)• The relationship between PK exposure and measures of efficacy and/or safety

Methodology:

This is a Phase 2a, randomized, double-blind, placebo-controlled, dose-ranging study in post-menopausal women in which the pharmacokinetic (PK) profile of ACER-801 at different doses is evaluated and the efficacy of ACER-801 (50 mg twice daily [BID], 100 mg BID, and 200 mg BID) will be compared to placebo in approximately 40 to 56 subjects (10 to 14 subjects per treatment arm).

Subjects will enter a Screening Period to determine eligibility. Subjects will be required to complete hot flash diaries for 2 weeks prior to randomization. Eligible subjects will be admitted to a Clinical Research Unit (CRU) on Day -1 and remain in the clinic from Day-1 until discharge on Day 16 after completion of treatment and all study assessments or upon withdrawal from the study. The study includes a 14-day safety follow-up assessment (Day 28).

Subjects will be randomized in a 1:1:1:1 ratio to ACER-801 per one of the following dosing schedules prior to dosing:

[figure not shown]
- 50 mg BID,
- 100 mg BID,
- 200 mg BID, or
- Placebo administered orally for 14 consecutive days (28 doses).

Blood samples for PK (plasma) assessment will be collected for concentrations of ACER-801 and its metabolite at predose, 0.5, 1.0, 1.5, 2.0, 2.5, 3.0, 4.0, 5.0, 6.0, 8.0, 12.0 (prior to evening dose), and 15.0 hrs post morning dose on Day 1 and Day 14, as well as predose (prior to morning dose) on Day 2 and Day 7. Plasma samples will also be collected 24 hrs (Day 15) and 48 hrs (Day 16) after the morning dose on Day 14.

Throughout the duration of the study (Day 1 through Day 16), subjects will be required to record the frequency and severity of hot flashes in a subject diary (continuous hot flash diary).

Electrocardiographs using the Mortara Surveyor will be collected on Day -1, Day 1, and Day 14.

During the study, subjects will be closely monitored for safety including assessments of AEs, 12-lead ECGs, atrial oxygen saturation using pulse oximetry, vital signs (sitting and standing blood pressure (BP), heart rate, oral body temperature, and respiratory rate), clinical labs, and physical examinations.

Target Population:

Approximately 40 to 56 post-menopausal women aged 40-65, inclusive, who experience an average of 7 to 20 moderate to severe hot flashes per day (subjects must have 7 or more hot flashes on each day during the 2-week period prior to randomization) as determined by a continuous hot flash diary where events are recorded for 2 weeks prior to randomization will be included in this study. Subjects will have no active, ongoing health conditions that could cause difficulty in interpretation of hot flashes categorized as moderate to severe.

Study Duration:

This study consists of a 28-day Screening Period, a 14-day Treatment Period and a 14-day Safety Follow-Up Period.

Number of Subjects (planned):

- Total: approximately 40 to 56 subjects will be enrolled for the study
- Per treatment: approximately 10 to 14 subjects per treatment arm including study drug and placebo
- Randomization: 1:1:1:1 (treatment: 50 mg BID, 100 mg BID, and 200 mg BID of ACER-801; placebo)

Inclusion Criteria:

To be eligible to participate in this study, subjects must meet all of the following criteria:

1. Post-menopausal female subjects 40-65 years of age, inclusive.
Menopause will be defined as:
 - a. At least 12 months of spontaneous, continuous amenorrhea, or
 - b. At least 6 months of spontaneous, continuous amenorrhea with serum FSH levels > 40 mIU/mL at screening, or
 - c. At least 6 weeks postsurgical bilateral oophorectomy with or without hysterectomy.
2. At baseline women:
 - a) With an average of ≥ 7 and ≤ 20 moderate to severe hot flashes/day for 2 weeks prior to randomization (per continuous hot flash diary). The minimum number of hot flashes on each day during the 2 weeks prior to randomization must be at least 7.
 - b) That have a change of $< 50\%$ in average 24-hour hot flash frequency 2 weeks prior to randomization.
 - Moderate: defined as sensation of heat with sweating, able to continue activity.
 - Severe: defined as sensation of heat with sweating, causing cessation of activity.
3. Able to understand and comply with the requirements of the study and sign Informed Consent forms.
4. Have not participated in any clinical research study evaluating another investigational drug, device or therapy within 30 days or within 5 half-lives (whichever is longer), of the investigational drug prior to consenting to study entry.

Exclusion Criteria:

To be eligible to participate in this study, subjects must not meet any of the following criteria:

1. Any active comorbid disease deemed by the investigator to be clinically significant, which could impact safety during study conduct including renal or hepatic impairment:
 - a. Serum creatinine laboratory value greater than 1.2 times upper limit of normal (ULN) reference range (after adjustment for age) at Screening or Day -1 or subjects with renal function glomerular filtration rate (GFR) < 60 mL/min/1.73m² based on the Chronic Kidney Disease Epidemiology Collaboration (CKD-EPI) equation.
 - b. Total bilirubin greater than upper limit of normal reference range (with the exception of Gilbert's Syndrome) and/or alanine aminotransferase (ALT) > 2 times ULN reference ranges and/or aspartate aminotransferase (AST) > 2 times ULN reference ranges at Screening or Day -1.

Laboratory values may be repeated once to confirm results.

2. Any active medicinal (pharmaceutical or homeopathic) therapy considered by the investigator to potentially cause hepatic impairment leading to elevated:
 - a. ALT and/or AST ranges.
3. Subjects with a prior medical history of or an increased risk of seizures, or who have a history of recent (within 6 months of Screening) head trauma that resulted in a loss of consciousness or concussion.
4. Any prior or ongoing history of arrhythmias.
5. Any ongoing cardiovascular disease including heart failure, coronary artery disease, uncontrolled hypertension, or uncontrolled diabetes (blood sugar level consistently over 100 mg/dL while fasting, higher than 180 mg/dL two hours after a meal, or random blood glucose levels higher than 200 mg/dL. Postmenopausal women with a history of hypertension must be medically cleared to participate in the study. Hypertension is defined as systolic blood pressure \geq 130 mg Hg or diastolic blood pressure \geq 80 mg over 3 readings on at least 2 different occasions, unless the participant receives medical clearance by her physician to participate in the trial.
6. Any clinically relevant ECG abnormalities at Screening, per Investigator discretion.
7. Use of any prohibited medications (see [Section 5.3.2](#)).
8. Any history of malignancy in the past 2 years.
9. Any active ongoing condition that could cause difficulty in interpreting vasomotor symptoms such as: infection that could cause pyrexia, pheochromocytoma, hypothyroidism, hyperthyroidism, carcinoid syndrome, alcohol abuse.
10. Body mass index (BMI) >35 kg/m².
11. Inability to complete questionnaires or continuous hot flash diary for any reason including psychiatric disorders and inability or unwillingness to use electronic devices.
12. History of hypothalamic dysfunction.
13. Any clinically significant or unstable medical or psychiatric condition that would interfere with the subject's ability to participate in the study including anxiety syndromes.
14. Any clinically significant abnormal laboratory test result(s) measured at Screening or on Day -1.
15. Participation in any clinical research study evaluating another investigational drug, device, or therapy within 30 days or within 5 half-lives (whichever is longer), of the investigational drug prior to consenting to study entry. If the subject is in an observational clinical study, no washout is required.
16. Subjects who, in the opinion of the investigator, should not participate in the study for any other reason.
17. Any known allergy or hypersensitivity to any of the ingredients in the study medication or to skin adhesives.
18. Current or planned use of other agents for treating hot flashes.
19. History or presence of alcohol abuse defined as consumption of more than 210 mL alcohol per week, or the equivalent of fourteen 4 ounce glasses of wine or fourteen 12 ounce cans/bottles of beer or wine coolers per week) within 6 months before Screening or positive alcohol test at Screening or Check-in (Day -1).
20. History or presence of substance abuse within the past 2 years or positive drug screen test at Screening or Check in (Day -1).
21. Presence of hepatitis B virus, hepatitis C virus (HCV), or human immunodeficiency virus (HIV) at Screening.
22. Current use or has used tobacco- or nicotine-containing products (e.g., cigarettes, cigars, chewing tobacco, snuff, vaping) within 30 days prior to first dose.
23. Known or suspected pregnancy on Day -1.

24. Positive COVID-19 test on Day -1.

Test Product, Dosage and Mode of Administration:

ACER-801 50 mg BID, 100 mg BID, 200 mg BID administered orally as 50 mg capsules
Oral

Reference, Dosage and Mode of Administration:

Placebo matched controls administered BID
Oral

Criteria for Evaluation:

Pharmacokinetics:

All blood samples for PK analysis will be analyzed by a central bioanalytical laboratory. Instructions for collection, processing, storing, and shipping of PK blood samples will be provided to the clinical unit by the bioanalytical laboratory.

Safety:

Subjects will be monitored throughout confinement and during the 2-week follow-up period for adverse reactions to the study treatments and/or procedures. Safety will be assessed by monitoring adverse events (AEs) and serious AEs (SAEs); vital signs; concomitant medications; physical examinations; ECGs; and clinical laboratory tests (hematology and coagulation, serum chemistry, and urinalysis). Ongoing AEs will be monitored (telephone call) until resolution or for 30 days, whichever is first. Abnormal lab findings will be closely monitored by the Sponsor and repeated as deemed necessary until resolution and followed up by the treating physician. All safety data will be reviewed by the Sponsor for any potential safety signals that would alter the safety profile of the molecule.

Statistical Methods:

Analysis Populations:

- The PK Population includes all randomized subjects who have evaluable PK samples.
- The Safety Population includes all randomized subjects receiving at least 1 dose of study treatment.
- The Modified Intent-to-Treat (mITT) Population includes all randomized subjects who receive study treatment with baseline and at least one post-baseline efficacy measurements.
- The Per-Protocol population includes all randomized subjects with baseline and efficacy measurement endpoint visits without any major protocol deviations that would have an impact on the efficacy measurements.

Pharmacokinetic Analyses:

Noncompartmental analysis (NCA) will be performed for the plasma concentrations of ACER-801 and its metabolite. Summary statistics for the PK parameters (C_{max} , t_{max} , AUC_{last} , AUC_{inf} , AUC_{τ} , Accumulation Ratio for C_{max} [AR C_{max}], Accumulation Ratio for AUC [AR AUC], Metabolite Ratio of C_{max} [MR C_{max}], Metabolite Ratio of AUC [MR AUC], $t_{1/2}$ of ACER-801 and its metabolite) will be determined for ACER-801 and its metabolite for the different dosing groups.

Safety Analyses:

All AEs/SAEs will be coded using the current version of the Medical Dictionary for Regulatory Activities to assign system organ class and preferred term classification, based on the original terms entered on the electronic case report form. The incidence of AEs will be summarized by system organ class, preferred term, relationship to study treatment, and severity for each study treatment. All AEs, including AEs that lead to premature discontinuation from the study and from study treatment SAEs, will be recorded.

All other safety measures including laboratory tests, vital signs, concomitant medication, medical history, physical examination, and ECG data will also be summarized descriptively (mean, standard deviation, median, minimum, and maximum). Laboratory tests will also be summarized by absolute and percent change from baseline and listed by clinical significance.

Concomitant medications will be coded using the most recent version of World Health Organization Drug Dictionary.

Efficacy Analyses:

The secondary endpoints are the change in frequency and severity of vasomotor symptoms and hot flash severity score at Week 1 and Week 2 relative to baseline.

Study Endpoints	
Primary Objective: The primary objectives of this study are to: 
• Evaluate the PK profile of ACER-801 and its metabolite at different doses• Evaluate the safety profile of ACER-801 at different doses	
Primary Endpoints	Assessments

• Pharmacokinetics (C_{max}, t_{max}, AUC_{last}, AUC_{inf}, $AUC\tau$, AR_{Cmax}, AR_{AUC}, MR_{Cmax}, MR_{AUC}, $t_{1/2}$ of ACER-801 and its metabolite)• Clinically significant changes in physical examination findings at Week 2 relative to Baseline• Clinically significant changes in clinical laboratory evaluations (hematology, coagulation, serum chemistry, urinalysis, hormones, bone density markers) during the 2-week treatment period relative to Baseline• Adverse events $\geq 5\%$• All SAEs and discontinuations	
• Noncompartmental analysis• Physical Examinations• Vital signs• Clinical laboratory assessments• AEs and SAEs
Secondary Objectives: The secondary objectives of this study are to: 
• Evaluate the effect of ACER-801 at different doses on the frequency of vasomotor symptoms associated with menopause compared to placebo• Evaluate the effect of ACER-801 at different doses on the severity of vasomotor symptoms associated with menopause compared to placebo• Evaluate the effect of ACER-801 at different doses on the hot flash severity score compared to placebo	
Secondary Endpoints	Assessments

• Change in frequency of vasomotor symptoms at Week 1 and Week 2 relative to Baseline• Change in severity of vasomotor symptoms at Week 1 and Week 2 relative to Baseline• Change in hot flash severity score at Week 1 and Week 2 relative to Baseline	
• Continuous hot flash diary entries throughout the study
Exploratory Objectives: The exploratory objectives of this study are to evaluate: 
• The effect of ACER-801 at different doses on change in hormones compared to placebo• Change in number of NTAs• Change in blood bone density marker concentration• Changes in blood markers associated with stress• Change in ECG variables (heart rate, RR, PR, QRS, QT, QTcF, and QTcB)• The relationship between PK exposure and measures of efficacy and/or safety	

Exploratory Endpoints	Assessments
Change in hormones relative to Baseline	
• LH• FSH• estradiol• testosterone• SHBG• ACTH• cortisol• TSH• T3 (Total and Free)• T4 (Total and Free)
Changes in the number of NTAs	Hot flash diary
Changes in bone density markers relative to Baseline	
• Bone specific alkaline phosphatase (BSAP)• Osteocalcin• Amino-terminal propeptides of type 1 collagen (P1NP)• CTX
Changes in blood markers associated with stress relative to Baseline	
• Catecholamines• Vasopressin• Gonadotropins• Prolactin• Insulin
Relationship between plasma exposure and changes in ECG variables	Graphical assessment of change in QT versus plasma exposure of ACER-801 and its metabolite.
Exposure-Response Relationship with Efficacy	Graphical assessment of efficacy or potential safety signals versus plasma exposure of ACER-801 and its metabolite.
Sample Size Justification: A sample size of approximately 10 to 14 subjects per arm (approximately 40 to 56 total) is considered sufficient to characterize the PK, safety and preliminary efficacy of ACER-801 based on study results from a dual neurokinin 1,3 receptor antagonists in postmenopausal women (Trower et al, 2020).	

TABLE OF CONTENTS

SPONSOR'S APPROVAL OF THE PROTOCOL	3
INVESTIGATOR'S AGREEMENT	4
STUDY PERSONNEL CONTACT INFORMATION	5
1 SYNOPSIS.....	6
TABLE OF CONTENTS.....	13
LIST OF TABLES.....	17
LIST OF FIGURES	17
LIST OF ABBREVIATIONS AND DEFINITIONS OF TERMS.....	18
2 INTRODUCTION	20
2.1 Background.....	20
2.2 Safety Data.....	21

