11.3.6 Mortara Surveyor for Electrocardiographs

A Mortara Surveyor will be used to collect ECG information (in triplicate) at timepoints coinciding with PK Samples. The extracted ECGs will then be blindly reviewed at a later time by an ECG core laboratory reader to determine changes in ECG variables (heart rate, RR, PR, QRS, QT, QTcF and QTcB). Graphical representations between ECG variables (e.g., QTcF) and plasma concentrations of ACER-801 and its metabolite will be generated.

The time and duration of ECG collection must be identical on Day -1, Day 1, and Day 14 and must be planned in relation to predose and 15 hrs postdose PK time points.

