12.5.5 ECG

- The change in ECG variables (heart rate, RR, PR, QRS, QT, QTcF, and QTcB) will be assessed.
- Relationship between plasma exposure and changes in ECG variables

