12.5.6 Exposure-Response Relationships

- Exploratory exposure-response relationships for efficacy (e.g., VMS), QT, and potentially safety relative to the plasma exposure of ACER-801 and its metabolite will be assessed.

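### The plan is inconsistent about the variable in the exposure-ECG analysis (uncorrected QT in two places, QTcF only as an example in a third) and specifies only graphs, so no exposure-based estimate with a confidence interval is planned

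*Combined protocol and SAP*

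**What the plan says.** Four places in the protocol bear on the variable.

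- Synopsis, exploratory endpoints table: the row is labelled "Relationship between plasma exposure and changes in ECG variables", but the assessment in that row is "Graphical assessment of change in QT versus plasma exposure of ACER-801 and its metabolite".
- Section 12.5.6 lists "Exploratory exposure-response relationships for efficacy (e.g., VMS), QT, and potentially safety", with no correction named.
- Section 11.3.6: "Graphical representations between ECG variables (e.g., QTcF) and plasma concentrations of ACER-801 and its metabolite will be generated".
- Section 12.5.5 repeats the general exposure endpoint and adds "The change in ECG variables (heart rate, RR, PR, QRS, QT, QTcF, and QTcB) will be assessed".

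On data, Section 11.3.6 states "A Mortara Surveyor will be used to collect ECG information (in triplicate) at timepoints coinciding with PK Samples", with blinded core-laboratory reading. It also requires the same time and duration of recording on Day -1, Day 1 and Day 14.

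On method, the synopsis and Section 11.3.6 speak of graphs, and Section 12.6.4 speaks of summary statistics. Section 12.6.2 summarises ECG data by mean, SD, median and range. Section 12 leaves analysis detail to a SAP to be approved before database lock and unblinding.

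**The concern.** Uncorrected QT shortens as heart rate rises and lengthens as it falls. If a drug changes heart rate, a plot of QT change against concentration mixes that effect with any effect on repolarisation, and can hide or mimic a QTc effect. The synopsis treats QT, QTcF and QTcB as separate variables, so someone programming from the endpoint table could reasonably plot raw QT.

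A graph, whatever its axis, also gives no slope, no predicted effect at the exposures reached and no confidence limit. This matters more than the exploratory label suggests. Safety is a primary objective, and by Sections 7.1 to 7.9 the scheduled 12-lead safety ECGs fall only on Screening, Day -1, Day 1 and Day 16. The Day 16 ECG comes about 36 hours after the last evening dose (48 h minus 12 h after the Day 14 morning dose). The Day 14 Surveyor recording is therefore the only scheduled ECG under repeated dosing after Day 1.

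**Working it through.** The plan states no QT threshold, heart-rate effect, baseline QTcF or SD, so it has no figure of its own to reproduce.

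**1. Which variable?**

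| Place | Variable related to exposure | Firm? |
|---|---|---|
| Synopsis, assessment cell | change in QT | yes |
| Section 12.5.6 | QT | yes, but in a list of domains |
| Section 11.3.6 | ECG variables, QTcF as example | no |
| Section 12.5.5 | ECG variables in general | no lead variable |

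Two places name QT, and none commits to QTcF.

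**2. What can a raw-QT plot hide?** Fridericia: QT = QTcF × (60/HR)^(1/3). Baseline heart rate and QTcF are my assumptions.

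- QTcF 400 ms at 65 bpm: QT = 400 × (60/65)^(1/3) = 389.5 ms.
- QTcF 410 ms at 70 bpm: QT = 410 × (60/70)^(1/3) = 389.5 ms. A true +10 ms in QTcF appears as no change.
- QTcF 400 ms at 70 bpm: QT = 400 × (60/70)^(1/3) = 380.0 ms. With QTcF constant, a 5 bpm rise from 65 bpm shows as 380.0 − 389.5 = −9.5 ms, and the reverse fall as +9.5 ms.

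The first pair was chosen to cancel, so the range matters more. The heart rate that leaves QT unchanged when QTcF rises by d is HR1 = HR0 × ((QTcF0 + d)/QTcF0)^3. For d = 10 ms:

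- smallest rise: 60 × (430/420)^3 = 64.39, a rise of 4.39 bpm;
- largest rise: 75 × (410/400)^3 = 80.77, a rise of 5.77 bpm.

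Over baselines of 60 to 75 bpm and QTcF 400 to 420 ms:

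| QTcF increase | Heart-rate rise that cancels it on a raw-QT plot |
|---|---|
| 5 ms | 2.2 to 2.9 bpm |
| 10 ms | 4.4 to 5.8 bpm |
| 20 ms | 9.0 to 11.8 bpm |

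**3. Would the rest of the plan show it?** Yes. Section 12.5.5 covers change in heart rate and QTcF separately. In the example above, those summaries would show +5 bpm and +10 ms.

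**4. What estimate is planned?** Means and SDs of ECG variables are within the plan. A slope, a model-based prediction at a given exposure, or a confidence interval for the exposure-ECG relationship is not stated anywhere.

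**5. What could the data support?** There are 13 PK times on each of Day 1 and Day 14, so up to 13 × 2 = 26 ECG-concentration pairs per subject, correlated within subject. For scale, the 90% CI half-width for one active arm against placebo at one timepoint is t(0.95, 2n−2) × SD × sqrt(2/n). With an assumed SD of change of 10 ms this is 7.75 ms at n = 10 and 6.45 ms at n = 14. It scales in proportion to the SD: an SD of 8 ms gives 6.2 and 5.2 ms, and an SD of 12 ms gives 9.3 and 7.7 ms. Comparisons timepoint by timepoint are therefore coarse beside a 10 ms effect. The precision of a pooled model was not calculated.

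**The case against.** The strongest reply is that the plan, read as a whole, already covers QTcF. Section 11.3.6 is the operational section, and the one variable it names for the concentration plots is QTcF. The row label in the synopsis and Section 12.5.5 both speak of ECG variables in general. In Section 12.5.6, QT stands beside efficacy and safety and may simply denote the QT domain. QTcF and heart-rate changes are assessed separately, so masking needs raw QT to be read alone, which no section prescribes. Detail is deferred to a SAP. In an exploratory analysis with 10 to 14 subjects per arm, a mixed model adds to the plan and does not correct an error. No objective claims to exclude a QT effect of a given size.

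Much of this stands. A reader might infer that the exposure-ECG endpoint is solely a plot of uncorrected QT, and that a real QTc prolongation would go unseen or that the ECG data yield no estimate at all. The documents do not support that: QTcF is a named example for the plots, and QTcF and heart rate have their own summaries. Nor does the absence of a model in Section 12 show that the final SAP lacks one.

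The inconsistency remains. Shorthand is a fair reading of Section 12.5.6, but a weaker one for the synopsis cell, because the synopsis lists QT, QTcF and QTcB separately. An example is not a commitment. Putting QTcF on the axis would still leave no estimate tied to exposure.

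**Conclusion.** The point holds in limited form. The protocol names uncorrected QT in two places, gives QTcF only as an example in a third and names no lead variable in a fourth. On a raw-QT plot alone, a rise of about 4.4 to 5.8 bpm would cancel a 10 ms QTcF increase. That figure rests on the Fridericia relation and the assumed baselines; the documents give no heart-rate effect of ACER-801, so whether such a rise would occur is unknown. The separate summaries would still reveal it.

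The more lasting gap is that the only exposure-ECG method stated is a graph, although the design collects triplicate ECGs matched to PK samples, a time-matched Day -1 recording and a placebo arm. The change is worth making before the SAP is approved, but the trial's primary conclusions do not depend on it.

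**What to change.** - In the synopsis endpoint table and Section 12.5.6, name change in QTcF from the time-matched Day -1 baseline as the lead variable, in line with Section 11.3.6. Plot heart rate against concentration beside it.
- In the SAP, prespecify one exploratory linear mixed-effects model of that change on ACER-801 concentration, with treatment (active or placebo) intercept, nominal time, baseline QTcF and random subject effects. Examine the metabolite separately, or jointly after checking its correlation with parent.
- Report the placebo-corrected predicted change with a 90% CI at the geometric mean Day 14 Cmax of each dose, labelled exploratory.
- Keep the graphs as checks on the model, in particular on linearity.

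No new data or procedures are needed. The cost is wording in two places, a small amount of analysis work and a linearity assumption that has to be checked.

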3.2 Secondary Objectives

The secondary objectives are to:

- Evaluate the effect of ACER-801 at different doses on the frequency of vasomotor symptoms associated with menopause compared to placebo
- Evaluate the effect of ACER-801 at different doses on the severity of vasomotor symptoms associated with menopause compared to placebo
- Evaluate the effect of ACER-801 at different doses on the hot flash severity score compared to placebo

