10.2 Exposure-Response Analysis

Graphical representation between efficacy measurements and plasma concentrations of ACER-801 and its metabolite will be generated to determine any potential relationships.

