11.3.8 Analytical Procedures

Whenever possible, all samples from each subject will be analyzed on the same standard curve. Standard and quality control samples will be included in each batch of study samples assayed. Samples with drug concentrations greater than the upper limit of the validated range of the assay will be diluted with the appropriate drug-free biological fluid and re-assayed; those which are below the lower limit of this range will be reported as being below the lower limit of quantification. The analysts will not have access to the randomization scheme.

Analytical results will be presented in tabular form in the final report and chromatographic and derived data will also be provided. Additionally, accuracy, precision, and linearity data for each standard curve and all quality control samples will be presented. Representative chromatograms and standard curve graphs will be included.

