12.6.4 Exploratory Analyses

The exploratory analyses will include summary statistics.

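### The exploratory exposure-response objective for efficacy is answered only by a plot, with no estimate and no rule for placebo women; if only treated women are plotted, it can look flat despite a real effect.

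*Combined protocol and SAP*

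**What the plan says.** The last exploratory objective (Synopsis and Section 3.3) is "The relationship between PK exposure and measures of efficacy and/or safety". Four places bear on how it is met:

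- Synopsis, Exploratory Endpoints: "Graphical assessment of efficacy or potential safety signals versus plasma exposure of ACER-801 and its metabolite".
- Section 10.2: "Graphical representation between efficacy measurements and plasma concentrations of ACER-801 and its metabolite will be generated to determine any potential relationships".
- Section 12.5.6: exposure-response relationships for efficacy, QT and possibly safety "relative to the plasma exposure of ACER-801 and its metabolite will be assessed".
- Section 12.6.4: "The exploratory analyses will include summary statistics".

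On who enters, Section 12.2 and the Synopsis say "The PK Population includes all randomized subjects who have evaluable PK samples". Section 11.3.8 says low assay values "will be reported as being below the lower limit of quantification". No rule sets these values, or placebo women, to zero exposure.

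Efficacy is also addressed apart from exposure. A secondary objective in Section 3.2 is to "Evaluate the effect of ACER-801 at different doses on the frequency of vasomotor symptoms associated with menopause compared to placebo", with parallel objectives for severity and the severity score. Section 12 sets alpha at 0.05 without multiplicity adjustment and promises an SAP before database lock and unblinding. The supplied document contains no statistical text beyond Section 12.

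**The concern.** A plot read by eye gives no effect per unit of exposure and no measure of uncertainty. In a study titled dose-ranging, those are what a later dose decision would draw on. Section 2.3 justifies only the top dose, on earlier safety data, and states no target exposure.

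Two gaps make the plot harder to read:

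- **Exposure measure.** The Synopsis and Section 12.5.6 speak of exposure, Section 10.2 of concentrations. The response is a change at Week 1 or Week 2, so a summary such as AUC suits it better than a single concentration. The text does not say which is meant.
- **Placebo.** If placebo women are left off, the plot starts at the 50 mg exposures. When most of the effect is already present there, the remaining rise is small against the scatter between women, and the natural reading is that there is no exposure-response.

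**Working it through.** **Plan's own figures.** 4 × 10 = 40 and 4 × 14 = 56, so the stated totals agree. Section 12.1 gives no effect size, SD or power, so no planned power can be reproduced. Everything below rests on assumptions.

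**Inputs from the protocol.** Doses 0, 50, 100 and 200 mg BID, 1:1:1:1; 10 or 14 per arm; alpha 0.05 (Section 12; two-sided assumed).

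**Assumed.** Residual SD 1; mean exposure proportional to dose; lognormal exposure with CV 50%; effect f(E) = Emax × E/(E50 + E), with exposure in dose-equivalent units, E50 = 50, and an effect of 1 SD at 200 mg BID. Detection means significance in the direction of benefit.

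**Why the treated-only plot is flat.** Emax = 1 × (50 + 200)/200 = 1.25. At the mean exposure of each dose:

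- 50 mg: 1.25 × 50/100 = 0.625 SD
- 100 mg: 1.25 × 100/150 = 0.833 SD
- 200 mg: 1.25 × 200/250 = 1.000 SD

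The rise from placebo to 50 mg is 0.625 SD. From 50 to 200 mg only 0.375 SD remains, and a plot of treated women shows only that part.

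**Share of simulated trials detecting the effect** (accurate to about two percentage points):

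| Analysis | n = 10 per arm | n = 14 per arm |
|---|---|---|
| Slope, treated women only | 0.15 | 0.19 |
| Straight line, placebo at zero | 0.46 | 0.63 |
| Saturating regressor, placebo at zero, true E50 | 0.65 | 0.80 |
| Same, E50 tenfold too low or sixfold too high | 0.58 | 0.73-0.74 |
| At least one dose versus placebo, unadjusted | 0.67 | 0.79 |

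With no true effect, each regression is significant in the benefit direction about 2.5% of the time, and the any-dose comparison about 6-7%.

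**Other curves** (same 1 SD and CV; the saturating regressor always uses E50 = 25; n = 10 / 14):

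| True E50 | Treated-only linear slope | Straight line, placebo at zero | Saturating, placebo at zero | Any dose versus placebo |
|---|---|---|---|---|
| 10 | 5% / 6% | 34% / 46% | 71% / 84% | 76% / 87% |
| 25 | 9% / 10% | 42% / 54% | 69% / 83% | 73% / 85% |
| 100 | 22% / 29% | 55% / 70% | 63% / 78% | 66% / 79% |

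A CV of 30% or 80% (n = 14, E50 = 10) gave 5-8% for treated-only slopes, linear or log-exposure, and 84-85% for the saturating form.

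**Reading by eye.** Take a correlation of 0.3 in 3 × 14 = 42 treated women. Fisher's z = 0.310 with standard error 1/√39 = 0.160. The limits 0.310 ± 1.96 × 0.160 are −0.004 and 0.623, so the 95% interval for the correlation is about 0.00 to 0.55. A plot does not show that range.

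**The case against.** The strongest reply is that this is the last-listed exploratory objective of a Phase 2a study whose primary objectives are PK and safety. Plots are a usual tool at that stage, and Section 12 defers detail to an SAP that may already add a model. This stands as to weight. It does not remove the gap in the supplied text, and the SAP is the right place to close it.

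Stronger readings are tempting, and the documents do not support them:

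- **That the trial can miss a saturating effect.** A reader might infer this from the flat plot. It does not follow. The objectives in Section 3.2 compare the doses with placebo, and a plateau does not hide a difference from placebo. Any-dose detection in the tables roughly equals that of the saturating model, at the price of more false positives.
- **That placebo women are excluded.** Sections 4.1 and 9.1 schedule PK samples without restriction by arm, and the PK Population does not exclude placebo. Whether a placebo sample counts as evaluable is undefined. A treated-only plot is one reading of silence.
- **That each efficacy contrast uses only the women in two arms.** Section 12.6.3 restates the endpoints and gives no model. ANCOVA is in the abbreviation list, and a four-arm ANCOVA would take its error variance from every arm.
- **That Section 10.2 plans to set a spot concentration against a weekly count.** Section 12.6.1 derives AUC and Cmax from the concentrations, so Section 10.2 may only be loosely worded.
- **That placing placebo at zero is enough.** A straight line with placebo at zero reaches only 0.46 and 0.63 in the main scenario. The assumed shape matters too.

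**Conclusion.** The concern holds as a minor, exploratory point. The supplied text promises a plot and summary statistics for exposure-response on efficacy, with no estimate, no interval, no settled exposure measure and no rule for placebo women. If placebo is left off, the analysis has little ability to show a relation that levels off: about 15% and 19% detection in the main scenario, against 58-65% and 73-80% for a saturating form with placebo at zero.

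What is at risk is the conclusion drawn from the exposure-response analysis, together with an estimate of where the effect levels off. Detection of efficacy is not at risk from this gap. All percentages depend on the assumed effect, SD, curve and CV, none of which the protocol gives. The wording gap depends on none of them.

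**What to change.** Keep the plots in the Synopsis row, Section 10.2 and Section 12.5.6, and show placebo women at zero exposure. Add before unblinding, in the protocol or SAP:

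> As an exploratory analysis, Week 2 change in hot flash frequency will be regressed on Day 14 AUCτ in all arms, with placebo subjects at zero exposure and baseline frequency as covariate. A linear form (slope, 95% CI) and an Emax form will be reported. For the Emax form, the half-maximal exposure will be fixed over a pre-specified grid, and the estimated maximum effect with its 95% CI will be given at each grid value. The same models on assigned dose will be reported beside them.

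The grid is needed because a saturating form has no single slope. In Section 10.2, name this exposure measure in place of concentrations.

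The cost is a few lines of text and one exploratory table. Day 14 AUCτ is already a PK endpoint (Section 12.3.1) with dense sampling (Section 9.1), so no new data are needed. The downsides are that a shape must be assumed, that exposure within an arm is not randomized (hence the dose-based models alongside), and that estimates will be imprecise at 10 to 14 per arm.
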